6.1.6.2. Premature Treatment Discontinuation Evaluations

Participants who discontinue study treatment early should remain on study and all evaluations should be performed as outlined in the SOE.

6.1.6.3. **Premature Study Discontinuation Evaluations**

Participants who discontinue study participation should undergo premature study discontinuation evaluations, as outlined in the SOE, within 7 days of study discontinuation. If study discontinuation occurs on or prior to Day 5, all procedures should be performed as described in the SOE for premature study discontinuation evaluations. If study discontinuation occurs on or between Day 5 and Day 28 all evaluations EXCEPT treatment adherence should be performed. If study discontinuation occurs after Day 5, all evaluations including site-collected NP swab(s) and blood collection should be performed.

For participants who prematurely discontinue from the study for reasons other than withdrawal of consent, sites will attempt to obtain information regarding vital status and endpoints per the SOE.

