10.7.3. Part 1 Analyses

Part 1 will be analyzed separately as an a priori powered study. A Statistical Analysis Plan will be developed that describes the analyses to address the study's primary, secondary, and exploratory objectives.

The following provides an outline of the methods for the main comparisons between randomized arms, particularly for the primary outcome measure.

Analyses involving randomized comparisons will include all randomized participants who received the first (confirmed) dose of study treatment, according to a modified intention-to-treat (m-ITT) approach. Participants who do not receive the first (confirmed) dose will be replaced. Unless stated otherwise, the date of randomization will be the time origin for analysis (Day 1). Additional per-protocol analyses may be performed, particularly for virology efficacy endpoints. Missing data are expected to be uncommon (<5 to 10% of participants). Losses to follow-up will be assumed non-informative and complete-case analyses will be conducted.

This is a virology proof-of-principle study, as such a type I error probability of 10% (α =0.10) will be used throughout, with no planned adjustments for multiplicity or primary or secondary endpoints. Throughout, all statistical tests will be two-sided and "exact" statistical procedures that do not rely on large sample assumptions will be applied where computationally feasible.

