10.7.3.1. Primary Outcome Measures

Virologic Efficacy: The distribution of days until first non-detectable SARS-CoV-2 viral RNA in NP swabs will be estimated for each randomized arm (drug versus placebo), using Kaplan-Meier methods with a corresponding exact stratified log-rank test (Part 1 only: to account for the "early" versus "late" time from symptom onset randomization strata). "Non detectable" will be defined as a viral load below the limit of quantification (BLOQ). Two consecutive non-detectable viral RNAs in NP swabs (or one negative with no further follow-up) will be required to achieve the event. The date of the first non-detectable will be the event date. Participants who prematurely discontinue the study before achieving non-detectable results will have follow-up for efficacy endpoints censored at the date of last measurement. Losses to follow-up will be assumed non-informative.

Safety and Tolerability: In order to measure the safety and tolerability of EIDD-2801, we will estimate by randomization arm the probability of 1) any AEs leading to early discontinuation of blinded treatment (active or placebo), 2) study drug-related discontinuation of treatment, 3) new grade 3 or higher AE (not already present at baseline), and 4) study drug-related new grade 3 or higher AE. The cumulative probability (i.e., risk) of each safety and each tolerability endpoint (4 endpoints) will be estimated using the Kaplan-Meier approach and stratified log-rank test will be employed for between trial arm comparisons (as outlined for the primary efficacy outcome). Follow-up will be right censored at the date of last known status and event times will be the date of first onset of the given endpoint (e.g., time to first AE leading to early discontinuation of blinded treatment).

The safety and tolerability profile of EIDD-2801 in humans is currently not fully characterized and descriptive participant-level listings of safety and tolerability events will be summarized. We will estimate 28-day risk function of each safety and tolerability endpoint with a corresponding 2-sided 90% confidence interval, with focus on the upper confidence limit for interpretation of results. To inform the design of future larger trials we will estimate the difference in probabilities

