1. INTRODUCTION

This SAP describes the statistical methods to be used during the analysis and reporting for study EIDD-2801-2003.

Study measurements and assessments, planned statistical methods, and derived variables are summarized in this plan. Planned tables, figures, and listings are specified. All decisions regarding final analyses, as defined in this SAP document, have been made prior to locking the database.

This SAP should be read in conjunction with the study protocol and electronic Case Report Form (eCRF). Any further changes to the protocol or eCRF may necessitate updates to the SAP. This SAP supersedes the statistical considerations identified in the protocol; where considerations are substantially different, they will be so identified. If additional analyses are required to supplement the planned analyses described in the SAP, they may be performed and will be identified in the Clinical Study Report (CSR).

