5.5.3. Derived Endpoints

• SARS-CoV-2 RNA

Efficacy Endpoint of SARS-CoV-2 RNA will be converted to log₁₀ scale. Listings will include the values in log₁₀ scale and in the original scale. For SARS-CoV-2 RNA values reported as below the limit of detection/quantification (the lower limit of quantification is 1018 copies/mL), 1017 copies/mL will be used in the analyses.

SARS-COV-2 RNA below the limit of detection/quantification will be considered as undetectable (negative) in the analyses.

• SARS-CoV-2 RNA Rate of Decline

The individual rate of SARS-CoV-2 RNA decline will be derived as Average Area under the Curve minus Baseline (AAUCMB, i.e., the average daily viral load value minus baseline) for the five time intervals of: D1-D3, D1-D5, D1-D7, D1-D14 and D1-D28 using the following formulas:

AAUC =
$$\frac{\sum_{i=1}^{n-1} (t_{i+1} - t_i) (\frac{x_{i+1} + x_i}{2})}{(t_n - t_1)} = \frac{AUC}{(t_n - t_1)}$$
, and
AAUCMB=AAUC – Baseline (x at time i=1)

where, x_i is the data value at the ith time point and t_i is the time value at the ith time point.

• Time to non-detectable SARS-CoV-2 viral RNA in NP swabs based on PCR

Two consecutive undetectable viral RNAs in NP swabs (or one negative with no further followup) will be required to achieve the event. The date of the first undetectable result will be the event date. If the subject only has undetectable viral RNA at the last on study assessment, it will be counted as event at the time of the last assessment. Subjects not achieving the event and who complete the study follow-up will be censored at the last viral RNA assessment. Subjects not achieving the event and dropped out before Day 28 will be censored at Day 28.

Time to un-detectable = Date of Event (Censored) – date of first dose+1

• Time to negativity of infectious virus isolation in NP swabs based on infectious virus isolation determined by isolation in Vero cell line culture

This endpoint will be derived similarly to time to undetectable viral RNAs in NP swabs based on PCR. Infectious virus will be measured at Days 1, 3, 5, and 7 and additional details will be provided in the CSR.

• Time to COVID Symptom Resolution:

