5.6. Missing Data and Outliers

For subjects who prematurely discontinue the study, all available data will be included in the analyses. The planned safety and efficacy analyses will be based on the reported data. An investigation will be made concerning the sensitivity of the results if extreme outliers are detected within the data.

Missing data will not be imputed. However, for adverse events with missing onset dates, treatment emergent flags will be assigned based on the imputation below:

Missing Adverse Event (AE) Onset Date

When a missing or partial onset date has been recorded, the following algorithm will be performed, designed to conservatively assign AEs as treatment emergent when the AE end date is not before the date of first dose.

- If the onset date is entirely missing, then the AE will be assigned as treatment emergent.
- If the year of onset only is provided and the year is the same as the year of first dose of any study drug, then this event would be treatment-emergent. If the year of onset only is

provided and the year is not the same as the year of first dose, then the onset date will be imputed as the 1st of January of that year to determine if the event is treatment emergent.

• If the month and year of onset are provided, and the month and year are equal to the month/year of first dose of any study drug, then this event would be treatment-emergent. In all other cases, the 1st day of the provided month/year of onset will imputed for the onset date to determine treatment emergent. Only if the provided month/year of onset is prior to the month/year of first dose would an event **not** be considered treatment-emergent.

AEs with end date prior to the date of first dose will not be considered treatment-emergent.

AEs with missing severity will be excluded from the by severity summaries. TEAEs with missing relationship to study drug will be considered to be probably related to study drug in the summaries.

Missing Data for SARS-COV-2 RNA Undetectable (Negative) Endpoint

Subjects with missing SARS-COV-2 RNA at a visit(s) will be imputed based on the available non missing SAS-COV-2 RNA data described in the table below:

Visit Before	Visit After	Imputation of Undetectable SAS-COV-2 RNA
BLQ/BLD	BLQ or BLD	Negative
>BLQ	BLQ or BLD	Positive
BLQ/BLD or missing	>BLQ	Positive[1]
Missing	BLQ or BLD	Missing
any value	Missing	Missing

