11. CHANGE FROM ANALYSIS PLANNED IN PROTOCOL

Due to lack of availability of subjects in the "early" time from symptom onset stratum, the between group comparison for the time to non-detectable SARS-CoV-2 viral RNA will be performed using an un-stratified log-rank test.

Statistical comparisons of safety endpoints between treatment groups in Part 1 will not be performed. All safety data will be presented descriptively.

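### The SAP censors event-free dropouts at Day 28 instead of at their last swab, contrary to the protocol, and does not list the change

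*SAP*

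**What the plan says.** Protocol 10.7.3.1 sets the rule for the Part 1 primary endpoint: "Participants who prematurely discontinue the study before achieving non-detectable results will have follow-up for efficacy endpoints censored at the date of last measurement". Protocol 10.7.3.2 repeats it for infectious virus.

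SAP 5.5.3 sets a different rule for dropouts: "Subjects not achieving the event and dropped out before Day 28 will be censored at Day 28". For completers who have not cleared, the same paragraph says: "Subjects not achieving the event and who complete the study follow-up will be censored at the last viral RNA assessment". Time to negative culture is derived in the same way, and the Day 28 sentence is repeated for time to symptom resolution.

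Protocol 10.7 and SAP section 1 both give the SAP precedence. SAP section 1 adds that "where considerations are substantially different, they will be so identified". Section 11 lists two changes. One concerns this same endpoint: "the between group comparison for the time to non-detectable SARS-CoV-2 viral RNA will be performed using an un-stratified log-rank test". The other drops the safety comparisons in Part 1. The censoring change does not appear, and the SAP gives no reason for it.

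**The concern.** Censoring should mark the last time a participant's status was known. Moving it to Day 28 asserts that someone who left after, say, Day 5 was seen to be uncleared at Days 7, 14 and 28. That amounts to imputing a positive result, with three consequences.

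- It conflicts with the protocol's assumption that losses are non-informative, and fits poorly with SAP 5.6, where "The planned safety and efficacy analyses will be based on the reported data" and RNA status after the last available visit is left missing.
- It is internally uneven: a completer who is still positive is censored at an actual swab, while a dropout with less data is credited with more follow-up.
- It penalises whichever arm loses more uncleared participants. Losses on active hide an effect; losses on placebo can create one.

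Part 1 carries the only formal efficacy hypothesis test (SAP 2.3), so the error falls on the one confirmatory result. In the pooled analyses the harm is limited to biased Kaplan-Meier estimates and descriptive p-values.

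**Working it through.** **Inputs.** Detection probabilities come from the Figure 8 table (protocol 10.5). Placebo at Days 3/5/7/14/28 is 88/71/52/10/0%. Active is placebo minus the risk difference (RD), floored at 0. Swabs are on Days 1, 3, 5, 7, 14 and 28. Part 1 has 22 per arm and a two-sided alpha of 0.10. Protocol 10.5 allows for up to 10% missing data; protocol 10.7.3 expects under 5 to 10%.

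**Assumptions not in the documents.** Dropout is independent of viral status and equally likely after Day 3, 5 or 7. Protocol 6.1.6.3 provides for a discontinuation swab: "Participants who discontinue study participation should undergo premature study discontinuation evaluations, as outlined in the SOE, within 7 days of study discontinuation". A negative result there counts as an event, so each range below runs from no such swab to every dropout giving one at the next scheduled visit.

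**The plan's own figure.** The SAP's 88% power at RD -35% reproduces with 19 evaluable per arm: 87.8% with a permutation log-rank test and 89.5% with the asymptotic test. The protocol attaches 88% to RD -30%, a separate discrepancy, so both effect sizes are shown.

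**A small example.** Take 22 in an arm. Two leave positive after Day 3; the other 20 clear as 2, 4, 4, 8 and 2 at Days 3, 5, 7, 14 and 28.

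- Last-swab censoring: the uncleared proportion at Day 14 is (20/22)(14/18)(10/14)(2/10) = 0.101, so clearance is 0.899; at Day 28 it is 1.00.
- Day 28 censoring: clearance is 18/22 = 0.818 at Day 14 and 20/22 = 0.909 at Day 28.

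**Bias in the placebo curve.** Under the Day 28 rule nobody is censored earlier, so Kaplan-Meier clearance at visit v is (1 - S(v)) - d × mean[S(L) - S(v)]. Here S is the detection probability, L the day of the last swab and d the dropout fraction. With d = 0.10:

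- Day 14, no discontinuation swab: 0.90 - 0.10 × (0.78 + 0.61 + 0.42)/3 = 0.840
- Day 14, swab at the next visit: 0.90 - 0.10 × (0.61 + 0.42 + 0)/3 = 0.866
- Day 28, no swab: 1 - 0.10 × (0.88 + 0.71 + 0.52)/3 = 0.930
- Day 28, swab: 1 - 0.10 × (0.71 + 0.52 + 0.10)/3 = 0.956

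The assumed values are 0.90 and 1.00. Last-swab censoring recovers them.

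**Effect on the test.** The log-rank statistic sums observed minus expected events, with expected events in arm 1 equal to (events at the visit) × n1/n. Dropouts kept in n1 raise the expected count but can add no observed event. Both rules were applied to the same simulated data (40,000 replicates per scenario, un-stratified asymptotic log-rank, Monte Carlo standard error at most 0.25 points):

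| Dropout, active v placebo | Last-swab rule | Day 28 rule |
|---|---|---|
| Power, RD -35%, 10% v 10% | 92% | 83–88% |
| Power, RD -35%, 5% v 5% | 92–93% | 87–90% |
| Power, RD -30%, 10% v 10% | 84% | 72–78% |
| Power, RD -35%, 10% v 0% | 92–93% | 75–85% |
| No effect, 10% v 10% | about 10% | 10–11% |
| No effect, 5% v 10% | about 10% | 10.5–11.4% |
| No effect, 0% v 10% | about 10% | 12–15% |
| No effect, 5% v 20% (beyond the plan) | about 10% | 13–20% |

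Rejections favouring active, nominally 5%, are 6.7–8.4% at 5% v 10% and 9–13% at 0% v 10%.

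**Culture.** SAP 5.5.3 measures infectious virus only to Day 7. The Figure 9 placebo values at Days 3/5/7 are 70/40/10%. With 10% dropout split between Days 3 and 5, Day 7 clearance reads 0.90 - 0.10 × (0.60 + 0.30)/2 = 0.855 without a discontinuation swab, and 0.90 - 0.10 × (0.30 + 0)/2 = 0.885 with one, against 0.90. Dropout after the Day 7 swab changes nothing. Symptom endpoints were not simulated.

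**The case against.** The contradiction and the omission from section 11 are hard to dispute. The case on the other side concerns size and scope.

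- *Power baseline.* The plan promises 88%, already net of missing data. Against that, 83–88% at RD -35% is a shortfall of 0 to 5 points, and 5% dropout costs almost nothing. This is a fair description of the practical loss. But the effect of the rule itself is the contrast on the same data, 92% against 83–88%.
- *Dropout pattern.* Missing data are not the same as leaving the study by Day 7. Spreading the 10% over Days 3, 5, 7 and 14 gives power of 85–89% at RD -35% and null rejection of 11–13% at 0% v 10%. The effects shrink but remain.
- *Replacement.* More participants may be enrolled, up to 204. That can restore power but does not remove bias.
- *Differential dropout.* Nothing in the documents predicts it, and with equal dropout type I error holds. That stands; the inflation is conditional.
- *Informative dropout.* If dropouts clear more slowly (illustration: 70% positive at Day 14, 30% at Day 28), true placebo clearance is 84% and 97%. Last-swab censoring reads 88–90% and 100%; the Day 28 rule reads 82–83% and 91–92%. Neither rule is then unbiased, and the Day 28 rule is closer at Day 14 but further off at Day 28. This supports a sensitivity analysis, not an unlisted change to the primary one.
- *Scope.* The protocol's rule sits in the Part 1 section; protocol 10.8 gives none for the pooled analyses, and the protocol sets no last-measurement rule for symptoms. The direct contradiction is therefore limited to Part 1 RNA and culture. For symptoms the argument is statistical only.
- *SAP 5.6.* Its table classifies results at missed visits and does not set censoring dates, so it is supporting evidence, not a second contradiction.

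**Conclusion.** The concern holds and should be corrected before the Part 1 analysis. The operative rule for the primary endpoint differs from the protocol, is not listed where the SAP says such changes will be identified, and treats unobserved time as observed non-clearance. Within the planned range of missing data the cost is moderate: up to about 7 points off placebo clearance at Day 28, roughly 4 to 9 points of power at RD -35% with equal 10% dropout, and a type I error of up to about 15% if all the dropout falls in one arm. These sizes rest on the Figure 8 curves, dropout independent of viral status and the assumed timing. Only dropouts who have not met the event are affected, and discontinuation swabs reduce the effect. The direction does not depend on the timing: estimated clearance falls in any arm with uncleared dropouts who would have cleared by Day 28, and the comparison tilts against the arm with more of them.

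**What to change.** In SAP 5.5.3, censor participants without the event at the date of their last evaluable assessment, counting the discontinuation swab, for both time to undetectable RNA and time to negative culture, as protocol 10.7.3.1 and 10.7.3.2 require. Use the same principle for dropouts in the symptom endpoints; the separate Day 28 rule there for hospitalised participants is not challenged and can stay. If the sponsor wants a Day 28 assignment for RNA, including one restricted to death or hospitalisation, present it as a labelled sensitivity analysis with its rationale. List any departure from the protocol that is kept in SAP section 11.

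The cost is one sentence of SAP text per endpoint family and one line of derivation code. No additional data are needed.

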4. SELECTION AND ENROLLMENT OF PARTICIPANTS

4.1. Inclusion Criteria

- 4.1.1. Able to provide informed consent prior to initiation of any study procedures.
- 4.1.2. ≥ 18 years of age at Screening.
- 4.1.3. Study treatment is expected to begin within ≤ 168 hours from first symptom onset.
- 4.1.4. Ability to swallow pills
- 4.1.5. Documentation of confirmed active SARS-CoV2 infection, as determined by a molecular or non-molecular ("rapid") test conducted at any clinic or laboratory that has a Clinical Laboratory Improvement Amendments (CLIA) certification or its equivalent from a sample collected ≤96 hours prior to study entry.
- 4.1.6. Experiencing at least one of the following SARS-CoV-2 infection symptoms at the time of enrollment: fever (can be subjective including feeling feverish or having chills) OR signs/symptoms of respiratory illness (including but not limited to upper respiratory congestion, loss of sense of smell or taste, sore throat OR lower respiratory illness cough, shortness of breath).
- 4.1.7. Agrees to not participate in another interventional clinical trial for the treatment of SARS-CoV-2 during the study period (28 days) unless hospitalized.
- 4.1.8. Agrees to not obtain investigational medications outside of the EIDD-2801 study.
- 4.1.9. Agrees to the sampling detailed in the SOE and to comply with study requirements including contraception requirements.

- 4.1.10. A female participant is eligible to participate if she is not pregnant or breastfeeding and at least one of the following conditions applies:
 - Is not a woman of childbearing potential (WOCBP)

OR

- Is a WOCBP and using a contraceptive method that is highly effective (a low user dependency method OR a user-dependent method in combination with a barrier method), or be abstinent from heterosexual intercourse as their preferred and usual lifestyle (abstinent on a long-term and persistent basis), as described in Appendix 2 during the intervention period and for at least 50 days after the last dose of study intervention. The investigator should evaluate the potential for contraceptive method failure (ie, noncompliance, recently initiated) in relationship to the first dose of study intervention.
- A WOCBP must have a negative highly sensitive pregnancy test (serum or urine) within 24 hours before the first dose of study intervention.
- Additional requirements for pregnancy testing during and after study intervention are located in Section 6.2.15.

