10.7.3.2. Secondary Outcomes

Safety: Occurrence of Grade 2 or higher AEs and drug related AEs will be evaluated using the same approach as outlined for the primary safety analysis in Section 10.7.3.1. We will describe and estimate all-cause mortality and hospitalization during the 28-day period from and including the day of the first (confirmed) dose of study treatment. The Kaplan-Meier approach described above will be applied to the endpoint of days until first hospitalization or death, and the 28-day risk function will be estimated as described for the primary safety endpoints.

Duration of fever, duration of symptoms, and duration of time to self-reported return to usual health will be summarized with descriptive statistics. Participant-specific durations of fever and symptoms will be compared between study arms using a stratified Wilcoxon rank-sum test. The distribution of days until improvement of all new or worsened COVID-19 symptoms will be compared between study arms using Kaplan-Meier methods with a corresponding exact stratified log-rank test (to account for the "early" versus "late" time from symptom onset randomization strata). New or worsened symptoms of COVID-19 may include feverishness, chills, myalgias, headache, sore throat, loss of sense of smell, loss of sense of taste, cough, and difficulty breathing. Improvement in these symptoms is defined as a decrease in all new or worsened symptoms (i.e., from severe/moderate severity to mild/absent/pre-COVID-19 severity, or a decrease in mild severity to absent). Participants who do not have complete symptom diaries due to hospitalization or death will be ranked in these analyses as having poorer outcomes than participants who survived without hospitalization.

Analyses for the additional objectives will be described in the SAP.

Virologic: The distribution of days until first non-detectable SARS-CoV-2 in NP swabs (i.e., infectious virus measurement) will also be estimated for each randomized arm (drug versus placebo), using Kaplan-Meier methods with a corresponding exact stratified log-rank test (to account for the "early" versus "late" time from symptom onset randomization strata). Participants who prematurely discontinue the study before achieving nondetectable results will have follow-up for efficacy endpoints censored at the date of last measurement. Losses to follow-up will be assumed non-informative.

Protocol EIDD-2801-2003 Ridgeback Biotherapeutics LP

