5.3.3. Safety Population

All subjects who are randomized and take at least 1 dose of study drug. Subjects will be analyzed according to the treatment they actually received. All the safety analyses will be performed using the safety population. The patient diary and clinical outcome (Ordinal Scale Clinical Improvement, medial visit) data will also be analyzed using the safety population.

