Time to COVID Symptom Resolution will be derived based on subject overall assessment of COVID symptoms with resolution defined as 3 consecutive assessments in a resolved state. For subjects with mild, no symptoms or no diary data at the baseline, the time to resolution is defined as the first time where subject overall assessment is no symptoms for 3 consecutive assessments . For subjects with moderate or higher severity at the baseline, the time to resolution is defined as the first time where subject overall assessment is mild or no symptoms for 3 consecutive assessments. Subjects who completed study and have reached the resolved state on the last 2 assessments will be considered as resolved on the day prior to the last assessment. Subjects who completed study and have reached the resolved state will be considered as resolved on the last assessment will be considered as resolved on the last assessment will be considered as resolved state on the last assessment will be considered as resolved state on the last assessment will be considered as resolved state on the last assessment will be considered as resolved state on the last assessment will be considered as resolved state on the last assessment will be considered as resolved state on the last assessment will be considered as resolved state on the last assessment will be considered as resolved state on the last assessment will be considered as resolved state on the last assessment will be considered as resolved state on the last assessment will be considered as resolved state on the last assessment will be considered as resolved state on the last assessment will be considered as resolved state on the last assessment will be considered as resolved state on the last assessment will be considered as resolved on the date of the last assessment.

Subjects not achieving symptom resolution and completing the study will be censored at date of last COVID symptom diary. Subjects not achieving the event and dropped out before Day 28 will be censored at Day 28. Subjects who do not achieve the event and do not complete the day 28 diary due to hospitalization will be censored at day 28.

Subject diary data collected within 28 days of first dose will be included in the derivation of the time to COVID symptom resolution endpoint.

Time to resolution (days) = Date of resolution (Censored) – date of first dose+1

• Time to patient reported general physical health of 3 or 4 (Very Good or Excellent)

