This endpoint will be derived similarly to the time to symptom resolution.

• Time to patient reported returned to the (Pre-COVID) health

This endpoint will be derived similarly to the time to symptom resolution.

• Time to resolution of upper respiratory tract symptoms (based on the worst severity of the 5 symptoms measured: Cough, Shortness of breath, Sore throat, Nasal obstruction and Nasal discharge)

This endpoint will be derived similarly to the time to symptom resolution.

• Time to resolution of common COVID symptoms (based on the worst severity of the 13 symptoms measured: Cough, Shortness of breath, Feeling feverish, Muscle aches, Diarrhea, Vomiting, Nausea, Headache, Sore throat, Nasal obstruction, Nasal discharge, Fatigue and Chills)

This endpoint will be derived similarly to the time to symptom resolution.

• Time to resolution of common COVID symptoms (based on the worst severity of the 12 symptoms measured: Cough, Shortness of breath, Feeling feverish, Muscle aches, Diarrhea, Vomiting, Nausea, Headache, Sore throat, Nasal obstruction, Nasal discharge and Chills)

This endpoint will be derived similarly to the time to symptom resolution.

• Time to resolution of Cough

This endpoint will be derived similarly to the time to symptom resolution.

• COVID related medical visit

A subject is considered to have a COVID related medical visit if the subject meets any of the following:

- 1. Hospitalized based on the Hospitalization CRF or any outpatient medical visit (including telemedicine visits)
- 2. Answered "Yes" to the Diary question 'Sought urgent medical care at an emergency room or clinic'
- 3. Answered "Yes" to the Diary question "Been hospitalized for at least 24 consecutive hours"

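### Participants without the symptom at baseline count as resolved at the start of the diary, which shortens and dilutes time to resolution of cough and, less so, of upper respiratory symptoms

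*SAP*

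**What the plan says.** SAP section 5.5.3 defines time to COVID symptom resolution from the participant's overall assessment, with "resolution defined as 3 consecutive assessments in a resolved state". Two baseline groups get different targets. Those rated moderate or worse must reach mild or none. The other group, introduced by "For subjects with mild, no symptoms or no diary data at the baseline", must reach none. In both, the event is the first time the state holds for three assessments in a row. For a participant with only two resolved assessments at the end of the study, the event "will be considered as resolved on the day prior to the last assessment", that is, on the first of the two. This indicates that an event is dated to the start of the run.

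The section then lists further endpoints, including "Time to resolution of Cough", a five-symptom upper respiratory composite, 12- and 13-symptom composites and two health-status endpoints. Each carries the line "This endpoint will be derived similarly to the time to symptom resolution". Under SAP section 5.3.3, diary "data will also be analyzed using the safety population", with no restriction to participants who had the symptom. SAP section 9.3 plans a Kaplan-Meier summary of these endpoints and names no test.

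The protocol words the endpoint differently. Sections 10.3 and 10.7.3.2 define improvement as a fall in severity, from severe or moderate to mild or absent, or from mild to absent. Section 10.7.3.2 adds: "New or worsened symptoms of COVID-19 may include feverishness, chills, myalgias, headache, sore throat". Section 10.8 also describes improvement as a change of state. None of the three gives a rule for a symptom that is absent at baseline.

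**The concern.** A participant who never coughs meets the cough rule with the first diary entries. Nothing has resolved, yet the Kaplan-Meier curve records an event at about Day 1 or 2. Inclusion criterion 4.1.6 does not prevent this for a single symptom. It asks for "Experiencing at least one of the following SARS-CoV-2 infection symptoms at the time of enrollment", and fever alone or loss of smell or taste alone is enough, so neither cough nor any of the five upper respiratory symptoms is guaranteed.

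Such events are expected at the same rate in both arms. They pull the medians down and draw the curves together. At stake is the secondary objective on severity and duration of self-reported symptoms: for cough, the reported median could describe people who had none.

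**Working it through.** The documents give no power, median or hazard ratio for any symptom endpoint, so there is no planned figure to reproduce. The check is how far a symptom-free fraction f moves the results.

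**Inputs from the documents.** 118 active and 54 placebo (sample assignment table, protocol section 3); 22 per arm in Part 1 (protocol 10.5) at two-sided alpha 0.10 (protocol 10.7.3); diary data to Day 28 (SAP 5.5.3).

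**Assumptions, not in the documents.** Placebo median about 10 days and hazard ratio 1.5 or 2.0 for resolution among the symptomatic; exponential times in whole days with the earliest event on Day 2; symptom-free participants have an event on Day 1; f from 0 to 50%; two-sided alpha 0.05 for the pooled set.

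**Medians by hand.** If a fraction f has an event on Day 1, the overall median falls where (1 - f) x S(t) = 0.5, so S = 0.5/(1 - f) among the symptomatic. The placebo time is 10 x log2(1/S). Divide by 1.5 for active, round up and add 1 day.

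- f = 0: placebo 10, giving Day 11; active 10/1.5 = 6.67, giving Day 8.
- f = 30%: S = 0.714; placebo 10 x 0.485 = 4.85, giving Day 6; active 4.85/1.5 = 3.24, giving Day 5.
- f = 50%: S = 1, giving Day 1 in both arms.

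**Simulation**, 4,000 trials per cell, log-rank test and Cox hazard ratio, 118 v 54, true hazard ratio 1.5. Each cell shows the SAP rule, then restriction to participants symptomatic at baseline:

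| f | Hazard ratio | Power | Medians, active/placebo (days) |
|---|---|---|---|
| 5% | 1.44 v 1.48 | 60% v 61% | 8/11 v 8/11 |
| 10% | 1.42 v 1.48 | 55% v 58% | 7/10 v 8/11 |
| 30% | 1.30 v 1.46 | 38% v 47% | 5/6 v 8/11 |
| 50% | 1.20 v 1.47 | 25% v 36% | 1/1 v 8/11 |

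The simulated medians at 30% and 50% match the hand calculation. The Monte Carlo standard error of a power figure is at most sqrt(0.5 x 0.5/4000) = 0.8 points. A repeat under the same sample size, hazard ratio, median and alpha gave 59% v 62% at 5%, 55% v 59% at 10% and 38% v 48% at 30%.

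**Cross-check of the restricted power (Schoenfeld).** Events d = (1 - f) x [118 x (1 - 2^(-27 x 1.5/10)) + 54 x (1 - 2^(-27/10))] = (1 - f) x 156.6. Power = Phi(ln 1.5 x sqrt(d x 0.686 x 0.314) - 1.96), where 0.686 = 118/172. This gives 65%, 50% and 38% at f = 0, 30% and 50%, within about 3 points of the simulated 64%, 47% and 36%.

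**Other settings.** With a true hazard ratio of 2.0 and f = 30%, pooled power is 81% v 91%; in Part 1 (22 v 22, alpha 0.10) it is 45% v 56%. With a true hazard ratio of 1.0, the SAP rule rejects in 4.8-5.9% of trials over all f and restriction in 4.9-5.8%, so there is no sign of inflation.

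**Chance imbalance.** The early events are equal between arms only on average. At f = 30%, the SD of the between-arm difference in symptom-free proportion is sqrt(0.3 x 0.7 x (1/118 + 1/54)) = 7.5 points in the pooled set and sqrt(0.3 x 0.7 x (2/22)) = 14 points in Part 1.

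**The case against.** The rule is written for the overall assessment, and criterion 4.1.6 makes a baseline rating of no symptoms uncommon there. The 12- and 13-symptom composites take the worst of many items, so few entrants lack all of them; the main exception is someone whose only symptom is loss of smell or taste, which the composites omit. This stands. A reader might infer that every resolution endpoint is seriously diluted, but the entry criterion does not support that.

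The quoted group also contains participants with mild symptoms or no baseline diary. Their target is the stricter one, which does not shorten the times of mild participants and can lengthen those of participants without a diary. This also stands: only the symptom-free part of the group creates early events.

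SAP section 9.3 plans Kaplan-Meier summaries only, and the SAP supersedes the protocol's statistics, including its log-rank tests for symptoms. Power is therefore a gauge of dilution here and not a planned output. The harm to medians and curves remains.

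Time to sustained absence in all treated participants is a legitimate quantity, and it keeps symptoms that emerge soon after entry. It does not, however, measure the duration of a symptom, which is the stated objective. SAP section 7.3 makes the symptom-free share visible by summarising baseline symptoms, and section 5.3.6 allows exploratory subgroups, but neither changes the planned medians.

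Finally, the protocol does not prescribe restriction to participants symptomatic at baseline. It defines improvement as a fall in severity and is silent on absent symptoms. What can be said is that the SAP rule departs from that definition and SAP section 11 does not list it.

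**Conclusion.** The point holds for time to resolution of cough and, to a lesser degree, for the five-symptom upper respiratory composite. Followed as written, the SAP counts participants without the symptom as resolved at about Day 1-2, and nothing else in it removes them. The overall endpoint and the larger composites should be little affected.

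The size depends on a fraction that the documents do not give. Under the stated assumptions, little changes at 5-10%. At 30%, the hazard ratio falls from about 1.46 to 1.30 and the placebo median from 11 to 6 days; at 50%, the median carries no information in either arm. These figures assume that everyone free of the symptom at baseline is an event at once. Anyone who develops it within the first assessments is not, so they are an upper bound for a given baseline fraction.

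A reader might fear a false-positive finding. The bias is toward no difference, on secondary endpoints; type I error and the primary virology endpoint are unaffected. This is an inexpensive improvement to the SAP, not a threat to the trial's main conclusion.

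**What to change.** In SAP section 5.5.3, analyse time to resolution of cough and of the upper respiratory composite in participants with that symptom or composite present at baseline and, for consistency, do the same for the other resolution endpoints. Report by arm how many lacked it, summarise new onset separately, and keep the all-participant analysis as a sensitivity analysis. Leave participants with no baseline diary under the stricter rule, with a sensitivity analysis that excludes them. State explicitly that the event date is the start of the qualifying run. List the departure from the protocol's improvement definition in SAP section 11.

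The cost is SAP wording and a few more tables; the restriction uses a pre-treatment variable already collected. Denominators become smaller for each symptom, and symptoms that emerge after entry move to a separate summary. In the simulations, restriction still had more power than the SAP rule at every symptom-free fraction from 5% upward, though the gain at 5% is no larger than simulation error in the main run.
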